## **8.6 Follow-up of Adverse Events and Serious Adverse Events**

### **8.6.1 Follow-up of Adverse Events with Onset during the Trial**

During the trial, the Investigator must follow-up on each adverse event until it is resolved or until the medical condition of the subject is stable.

After the subject's last visit, the Investigator must follow-up on any AE classified as serious or considered to have a reasonable possible causality to the IMP until it is resolved or until the medical condition of the subject is stable. All such relevant follow-up information must be reported to Ferring. If the event is a chronic condition, the Investigator and Ferring may agree that further follow-up is not required.

### **8.6.2 Collection of Serious Adverse Events with Onset after Last Visit in the Trial**

If an Investigator becomes aware of an SAE after the subject's last visit, and he/she assesses the SAE to have a reasonable possible causality to the IMP, the case will have to be reported to Ferring, regardless how long after the end of the trial this takes place.

## 9 STATISTICAL METHODS

The Global Biometrics Department of Ferring Pharmaceuticals A/S will be responsible for the statistical analyses. All analyses will be detailed in a separate Statistical Analysis Plan.

The pharmacokinetic parameters specified will be computed by the Department of Experimental Medicine, Ferring Pharmaceuticals A/S. Analysis of PK at end of study will be performed under the responsibility of Global Biometrics.

### 9.1 Determination of Sample Size

Part 1: No formal sample size calculation has been made. However, the number of patients (six) is considered sufficient to provide adequate information about the safety and tolerability of FE 204205, and thus inform about the suitable dose to evaluate in part 2.

Part 2: Since this is the first exploratory evaluation of the efficacy of FE 204205 on reducing portal pressure, the sample size and power calculations were performed by evaluation of the intra-group difference (before and after treatment with FE 204205). Assuming, based on the literature, a standard deviation (SD) of relative change from baseline of 12 % (see table below), a sample size of 14 patients on active treatment was deemed sufficient to detect a within-group 10 % reduction in HVPG, with  $\alpha = 0.05$  and  $1-\beta = 0.8$ . Taking into consideration that it occasionally can be technically challenging to assess HVPG, a total of 20 patients (16 on FE 204205 and 4 on placebo) are targeted (4:1 randomisation).

**Table 9-1 SD of relative (%) and absolute change from baseline in HVPG**

Reference	Inv Drug	SDs of %Change in HVPG	SDs of Change in HVPG (mmHg)
Escorsell et al. (7)	Terlipressin	9%, 12%	
Abraldes et al. (8)	Simvastatin	9%, 12%	
Berzigotti et al. (9)	NCX-1000	(~13 %)	2.2 mmHg* (baseline 17.1 mmHg)
Reverter et al. (10)	Saproterin	(~14 %)	2.2 mmHg* (baseline 16.0 mmHg)

\*derived from reported mean change, sample size and p-value (two-sided paired t)

A reasonable estimate of the SD would be 12% (also assumed by Reverter et al. (10) in their power calculations)

### 9.2 Subject Disposition

All subjects screened and dosed in Part 1 and all subjects screened and randomised in Part 2 will be accounted for. All post-dosing and post-randomisation discontinuations will be summarised by time of, and reason for, discontinuation. The number of subjects screened but not found eligible will be stated in the report but otherwise not accounted for.

### **9.3 Protocol Deviations**

The rating of protocol deviations will be decided on the basis of a review of the data before unblinding of the data and the declaration of 'clean file' and database lock. Major protocol deviation criteria will be specified in the statistical analysis plan.

### **9.4 Analysis Sets**

#### **9.4.1 Full Analysis Set**

The full analysis data set (FAS) comprises all subjects that are dosed at least once and is analysed according to the actual treatment received.

#### **9.4.2 Per Protocol Analysis Set**

The per protocol (PP) analysis set comprises all dosed patients with no major protocol deviations and with HVPG $\geq$ 12 mmHg at baseline. For subjects encountering a major protocol deviation after study treatment has been initiated, data after the point at which the first deviation occurs will be excluded from all evaluations. Final decisions for exclusion of subjects/subject data from the PP analysis set will be made when a clean database is available to review ahead of database lock. The PP analysis set will be used for the PK analysis with the exception that specific subjects may be excluded if certain PK parameters cannot be estimated with sufficient precision (criteria for which will be further detailed in the Statistical Analysis Plan)

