## Statistical analyses

The statistical analysis will include descriptive statistics reflecting the explorative nature of the study. In general, the data will be presented by dose level in Part 1 and by treatment group in Part 2.

No single primary endpoint has been identified, and there will be no multiplicity adjustments for the statistical analysis comparisons performed. In Part 2, the statistical analyses are based on the assumption that a placebo effect is negligible, so the primary statistical analyses will be performed using analyses of covariance of the change and relative change from baseline in the pharmacodynamic parameters adjusting for the respective baseline values to assess the significance of comparisons with baseline within each group (in the treatment group to assess the treatment effect and in the placebo group to assess the assumption of a negligible placebo effect). Secondary inferential statistics will be computed between placebo and active treatment using an analyses of covariance with treatment group as an additional factor.

The pharmacodynamic and safety endpoints will be analysed for the safety analysis set. The PK analyses will be performed for the PP analysis set.

HVPG will be derived as the average of the duplicate assessments, separately calculated for each scheduled assessment, of the difference between WHVP and FHVP (WHVP- FHVP).

HVPG and other haemodynamic variables will be assessed as change from baseline to 1 and 2 hours post dose separately analysed for each treatment group, and compared between groups.

Non-compartmental pharmacokinetic analysis of FE 204205 will be performed.

Changes in safety parameters will be evaluated by subject listings and descriptive statistics.

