### **3.2 Planned Number of Trial Sites and Subjects**

The trial will be conducted at one site, University of Barcelona, Hospital clinic, Spain, including patients with cirrhotic portal hypertension, 6 patients in Part 1 completing all Visit 2-assessments, and approx. 20 patients in Part 2, at least 18 of which in Part 2 with HVPG  $\geq$  12 mmHg at baseline.

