### **3.5.6 Selection of the Trial Population**

Subjects with cirrhotic portal hypertension and anticipated HVPG  $\geq 12$  mmHg, are chosen as trial population since this is the target population. Measures will be taken to reach a balanced ratio between genders (i.e. at least 1/4 of each gender) in the trial.

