#### 4.1.1 Inclusion Criteria

1. Signed written informed consent
2. Male or female patient, 18-65 years of age with confirmed evidence of cirrhosis
3. From medical history anticipated HVPG  $\geq 12$  mmHg
4. Negative pregnancy test at Screening and on Day -1
5. Agrees to use an adequate method of contraception during the study until the follow-up visit, if not abstinent. Adequate methods of contraception include condom with or without spermicidal gel (adequate only for male participants), intrauterine device, surgical sterilisation, vasectomy, oral contraceptive pill associated with inhibition of ovulation, depot progesterone injections
6. Negative urine drug screen and alcohol urine test at Screening and on Day -1

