#### **9.6.2.8 Pharmacokinetics**

The pharmacokinetic analysis will be based on the PP analysis set and performed by Department of Experimental Medicine, Ferring Pharmaceuticals A/S. The pharmacokinetic parameters will be calculated by non-compartmental analysis (NCA) using the software Phoenix WinNonlin® (Pharsight Corporation, U.S.A.). Actual sampling time points relative to dosing (i.e. starting time of dose infusion) will be used for the NCA and on the individual plots of plasma concentration versus time. Scheduled time points will be used in the descriptive summaries and summary plots of the data. Plasma concentration values below lower limit of quantification (LLOQ) and missing values (e.g. no blood sample collected or no value obtained at analysis) will be excluded from the NCA. Values below LLOQ will be represented by ‘LLOQ/2 in summary tables and plots of the data. No formal analysis of “outliers” is planned.

From the plasma and urine concentration-time data of FE 204205 the following parameters will be estimated, if possible: AUC, AUCt, % Extrap AUC, Cmax, tmax, CL, Vz, λz, t1/2, MRT, Ae and CLR.

Selection of data points for calculation of  $t_{1/2}$  via  $\lambda_z$  will be based on the following considerations:

- AUC will be calculated by the linear trapezoidal method
- The automatic range selection used in Phoenix WinNonlin® will be used to propose an optimal number of time points to use for the calculation of  $\lambda_z$ .
- At least three samples above LLOQ obtained during the log-linear elimination phase will be included in the calculation of the  $\lambda_z$ .
- The final selection of samples for calculation of  $\lambda_z$  will be based on visual inspection of log concentration-time plots of individual profiles.

Pharmacokinetic parameters will be presented by treatment (only for subjects receiving active treatment) with number of measurements, number of missing data, mean, standard deviation, median, minimum, maximum, geometric mean, and %CV (based on untransformed data) for geometric mean (for AUC and  $C_{max}$ ). For  $t_{1/2}$ , the harmonic mean will be listed instead of the geometric mean. For  $t_{max}$  the geometric mean and the CV% will be omitted.

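### PK is analysed on the per-protocol set, which requires a measured baseline HVPG of at least 12 mmHg, so correctly enrolled patients can lose valid concentration data from the PK analysis

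*Combined protocol and SAP*

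**What the plan says.** Three places put PK on the per-protocol (PP) set. The synopsis, under Statistical analyses, says: "The PK analyses will be performed for the PP analysis set". Section 9.6.2.8 says: "The pharmacokinetic analysis will be based on the PP analysis set". Section 9.4.2 says: "The PP analysis set will be used for the PK analysis with the exception that specific subjects may be excluded", the ground for that exception being parameters that cannot be estimated with enough precision.

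Section 9.4.2 also defines the set. It "comprises all dosed patients with no major protocol deviations and with HVPG" of at least 12 mmHg at baseline.

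Entry is looser. Inclusion criterion 3 in section 4.1.1 reads "From medical history anticipated HVPG" of at least 12 mmHg. Section 3.5.6 describes the population by the anticipated value too, and says such subjects "are chosen as trial population since this is the target population".

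Section 3.2 sets the numbers. Part 2 takes about 20 patients, "at least 18 of which in Part 2 with HVPG" of at least 12 mmHg at baseline. Part 1 has "6 patients in Part 1 completing all Visit 2-assessments", with no HVPG requirement attached. Section 4.6 replaces only Part 1 subjects who withdraw early.

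**The concern.** The PP definition makes a haemodynamic reading a condition for using concentration data. A patient who met every entry criterion, received FE 204205 and gave a full set of samples has no protocol deviation merely because the measured HVPG came out below 12 mmHg. That patient still leaves the PK set. So does a patient with no usable baseline HVPG, and section 9.1 acknowledges that HVPG can be technically difficult to obtain. A baseline HVPG reading does not show whether a concentration profile is valid.

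The pharmacokinetics of FE 204205 after intravenous infusion is a stated objective (section 2.1). Section 1.2 says this is the first study of the compound in patients with cirrhotic portal hypertension. At most 22 patients are planned to receive it (6 in Part 1 and 16 in Part 2), so each discarded profile is a noticeable share of the information.

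**Working it through.** **The plan's own figure.** Nothing is calculated for PK. The only calculated figure is the 14 active patients for the HVPG change in section 9.1. It reproduces with a two-sided paired t test at alpha 0.05, a 10% reduction and an SD of 12% (power 0.822 at 14 and 0.788 at 13). It has no bearing on this point.

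**1. Entry against PK membership**

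| Question | Rule | Source |
|---|---|---|
| Who may enter? | HVPG ≥12 mmHg anticipated from history | 4.1.1 |
| Who is in PP? | No major deviation and measured baseline HVPG ≥12 mmHg | 9.4.2 |
| Who is in PK? | PP, less subjects with imprecise parameters | 9.4.2 |

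The PK exception in 9.4.2 only adds exclusions. It does not bring back a patient whom the HVPG condition removed.

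**2. Does other text lift the condition?** Section 9 announces a separate SAP. What the protocol explicitly leaves to it is the major-deviation criteria (9.3) and the PK-precision criteria (9.4.2). The HVPG condition is already fixed. Section 9.6 says in general terms that endpoints use the FAS and PP sets, but the PK-specific text in 9.6.2.8 names PP alone.

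**3. Part 2.** Inputs are about 20 patients, 16 active and 4 placebo (9.1), with at least 18 having baseline HVPG ≥12 mmHg (3.2).

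- Patients allowed to lack the value, whether low or missing: 20 − 18 = 2.
- Worst case, both on active: 2/16 = 12.5% of active profiles lost.
- If exactly 2 lack it, unrelated to allocation, the expected number on active is 2 × 16/20 = 1.6. The probabilities of 0, 1 and 2 are 0.03, 0.34 and 0.63.
- The half-width of a 95% CI for a mean log parameter, in log-SD units, is t(0.975, n−1)/√n. This gives 0.533 for n = 16, 0.554 for n = 15 and 0.577 for n = 14.
- Widening: 0.554/0.533 = 1.039 with one lost, and 0.577/0.533 = 1.084 with two lost.
- The CI factor around a geometric mean is exp[half-width × √ln(1+CV²)]. The documents give no CV. From n = 16 to n = 14 it moves from 1.111 to 1.121 at an assumed 20%, from 1.169 to 1.185 at 30%, and from 1.286 to 1.314 at 50%.

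The plan reports PK descriptively, so these intervals only illustrate precision.

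**4. Part 1.** Inputs are the dose plan in Table 5-1, PK sampling on Days 1 to 3 (7.1.9), and HVPG first measured pre-dose on Day 3 (Table 6-1, footnote 8). A profile here is one patient on one dosing day.

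- Planned profiles: 6 × 3 = 18.
- By dose: 3 at 0.01 mg, 6 at 0.025 mg, 6 at 0.05 mg and 3 at 0.1 mg.
- One excluded completer removes 3/18 = 16.7% of profiles: 1 of 6 at each middle dose, and 1 of 3 at either the lowest or the highest dose.
- The excluding value is obtained only on Day 3, after two of the three PK days have been completed.
- A completer with low HVPG has not withdrawn, so section 4.6 triggers no replacement.

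**The case against.** **It is a deliberate and consistent choice.** The three PK statements agree, HVPG of at least 12 mmHg is the intended population, and section 3.2 sets a quota on the measured value. Describing PK in patients confirmed to be in that population is a legitimate aim. It stands that this is not an internal contradiction. But section 3.5.6 defines the target by anticipated HVPG, no reason is given for restricting PK, and a subset summary would serve the same aim without discarding data.

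**Section 9.6 may keep PK on the FAS as well.** Section 9.6.2 lists PK and metabolites among the endpoints to which that general sentence applies. The specific text in 9.6.2.8 is the likelier rule, but this is interpretation. The announced SAP, which is not in the text reviewed here, could also settle it.

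**The trial is exploratory and the Part 2 effect is small.** This stands.

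A reader might also infer more than the documents support:

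- *That HVPG is unrelated to PK.* The documents do not show this. Severity of portal hypertension might relate to clearance. If it does, that is a reason to keep these patients and show the subset.
- *That Part 1 precision collapses.* The half-width formula gives 2.484 at n = 3 and 8.985 at n = 2, a 3.6-fold increase. The plan computes no PK intervals, and one from 3 patients is already uninformative. The useful statement is 2 profiles instead of 3.
- *That a Part 1 loss is likely.* At assumed rates of 5%, 10% or 20% below 12 mmHg, 1 − (1 − rate)^6 gives 26%, 47% or 74%. The spread comes wholly from the assumption. The only planning figure is the Part 2 allowance of 2 in 20.
- *That PK-PD data are lost.* Section 9 assigns no analysis set to PK-PD, so this cannot be claimed.

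**Conclusion.** The point holds as a fault in the choice of analysis set. As written, the plan removes correctly enrolled patients with valid concentrations from PK because of a measurement that does not decide whether those concentrations are valid.

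The Part 2 cost is modest, at about 8% on interval width in the worst case. That assumes 20 patients, the HVPG target met, and no other PP exclusions. Part 1 is more exposed, because a single exclusion takes one third of the planned data at an end dose. That count assumes escalation as planned; section 3.1.2 allows a dose to be repeated, and section 5.1.1.1 allows a modified regimen. How often it would happen cannot be stated from the documents. The conclusion also takes 9.6.2.8 to govern over 9.6, and assumes that the separate SAP follows the protocol.

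The change is worth making because the dataset is very small and the remedy costs almost nothing. Nothing here suggests that the PK results would be biased or unusable.

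**What to change.** Define a PK analysis set: all subjects who received FE 204205 and have evaluable post-dose concentrations, with no HVPG criterion. Exclude only data affected by deviations that invalidate PK, and parameters that cannot be estimated.

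Name this set in the synopsis (Statistical analyses), in section 9.4.2 and in section 9.6.2.8, and add an exception for PK to the general sentence in section 9.6. Show the subset with baseline HVPG ≥12 mmHg as a sensitivity PK summary. Keep the HVPG criterion for the per-protocol analyses of portal haemodynamics, where it belongs.

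The cost is one definition, four matching text edits and one extra summary. No patients, samples or procedures are added.

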#### **9.4.3 Safety Analysis Set**

The safety analysis set comprises all subjects that received at least one dose of IMP and is analysed according to the actual treatment received.

### **9.5 Trial Population**

Presentations will be based on the FAS and the PP datasets, if they are identical only the FAS dataset will be presented.

#### **9.5.1 Demographics and other Baseline Characteristics**

Descriptive statistics of demographics and other baseline characteristics will be presented separately for Part 1 and 2. For Part 2 also separately by treatment group to assess the degree of similarity achieved.

#### **9.5.2 Medical History, Concomitant Medication and Other Safety Evaluations**

Medical history (recorded at the screening visit) will be coded using the latest version of the MedDRA. Prior and concomitant medication will be summarised by ATC classification 1st level (alphabetically), ATC classification 2nd level (in decreasing order of frequency).

Concomitant medication and relevant medical history will be presented by descriptive statistics, by part and treatment.

## 9.6 Endpoint Assessments

Endpoint assessment will be based on the FAS data set and the PP dataset.

### 9.6.1 General Considerations

All endpoints (see Section 9.6.2) will be analysed using descriptive statistics. In general, the data will be presented by dose level and time point in part 1 and by treatment group and time point in Part 2.

Inferential analyses on change and relative change from baseline in systemic and portal haemodynamic variables from Part 2 of the study will be conducted by using an Analyses of Covariance (ANCOVA) adjusting for the respective baseline value per treatment arm and time point. The focussing on mean change from baseline is based on the assumption the of a negligible placebo effect as reported in e.g. (7,8). Nevertheless, placebo-subtracted treatment effects will also be inferred (despite of limited power) using ANCOVA with treatment group as an additional factor.

### 9.6.2 Endpoints

The following endpoints, without differentiation between primary and secondary endpoints, will be analysed:

- Type, frequency and intensity of adverse events (AEs)
- Electrocardiogram (ECG) (intervals, rhythm, and morphology)
- Clinical chemistry, haematology and urinalysis
- Venous blood gases including lactate
- Systemic haemodynamics: Blood pressures and heart rate by non-invasive measurements, pulmonary capillary wedge pressure (PCWP), pulmonary artery pressure (PAP), right atrial pressure (RAP), mean arterial pressure (MAP), and cardiac output (CO) by pulmonary artery catheterisation. CO, MAP, and RAP will be used for calculation of the systemic vascular resistance (SVR)
- Portal haemodynamics by hepatic vein catheterization: Free hepatic venous pressure (FHVP), wedged hepatic venous pressure (WHVP), and inferior vena cava pressure (IVC). WHVP and the FHVP will be used for calculation of the hepatic venous pressure gradient (HVPG)
- Pharmacokinetics: AUC, AUCt, % Extrap AUC, Cmax, tmax, CL, Vz, λz, t1/2, MRT, Ae and CLR
- Metabolites in plasma and urine
- Blood and urinary biomarkers: Renin, aldosterone, norepinephrine, atrial natriuretic peptide (ANP), brain natriuretic peptide (BNP), urine creatinine, urine sodium, and urine osmolality.

#### 9.6.2.1 Systemic and portal haemodynamics

Supine blood pressure, pulse, and body temperature (absolute values) will be summarised by treatment and time point. Shift tables will be presented for changes from baseline, and will be

summarised by treatment. Abnormal values will be flagged in a subject listing. PCWP, PAP, RAP, MAP, CO, and SVR will be summarised by treatment and time point.

#### **9.6.2.2      ECG**

All ECG data (heart rate, PR interval, RR, QRS, QT/QTc) will be listed for each subject and summarised by treatment and time point. In addition, ECGs will be categorised as “normal”, “abnormal, not clinically significant”, or “abnormal, clinically significant” (as judged by the Investigator) and summarised.

#### **9.6.2.3      Clinical laboratory variables**

Clinical chemistry and haematology parameters will be summarised in terms of absolute values and changes from baseline to each scheduled post-baseline time point. Shift tables will be presented for changes in category (below, within, or above the normal range) from baseline, presented by treatment. Urinalysis parameters will be summarised by treatment and time point.

#### **9.6.2.4      Adverse events**

Adverse events (AE) will be coded according to the latest version of MedDRA. All data will be listed by subject. Only treatment emergent AEs will be presented in summary tables. Separate data listing will be provided for AEs that are defined as pre-treatment or post-treatment emergent.

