### Visit 3 (Follow-up, Day 5 to Day 12)

A follow-up visit will be performed 4-11 days after the administration, and will be considered end of study. At this visit a physical examination, assessment of vital signs and 12-lead ECG recording will be performed, pregnancy test, and samples for clinical laboratory parameters will be collected ([Table 6-2](#)).

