#### 7.1.2 Vital Signs

Vital signs comprising systolic and diastolic arterial blood pressure (including calculation of mean arterial pressure) and pulse will be assessed at screening, on Day -1, pre-dose, every 5 min until 30 min after start of infusion, then every 10 min until 1 hour after start of infusion, then every 15 min until 2.5 hours after start of infusion and thereafter 3, 4, and 6 hours after start of infusion on Days 1-3, and in the morning of Day 4 as well as at the follow-up visit in Part 1. Body temperature will be measured pre-dose and 6 hours after start of infusion on Days 1-3 in Part 1.

In Part 2, vital signs will be assessed at screening, on Day -1, pre-dose, every 5 min until 30 min after start of infusion, then every 10 min until 1 hour after start of infusion, then every 15 min until 2.5 hours after start of infusion and thereafter 3, 4, and 6 hours after start of infusion on Day 1, in the morning of Day 2, and at the follow-up visit. Body temperature will be measured pre-dose and 6 hours after start of infusion on Day 1.

Systolic and diastolic blood pressure will be measured after the subject has been in supine position for at least 5 minutes. All recordings will be performed using validated standard equipment. Clinically significant abnormal findings will be reported as AEs. Additional vital signs assessments may be collected by the Investigator for safety reasons.

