#### Treatment Emergent Adverse Event

A treatment emergent adverse event is any AE occurring after the administration of the IMP and within the time of residual drug effect, or a pre-treatment adverse event or pre-existing medical condition that worsens in intensity after administration of the IMP and within the time of residual drug effect.

The time of residual drug effect is the estimated period of time after the administration of the IMP, where the effect of the product is still considered to be present based on pharmacokinetic (PK), pharmacodynamic (PD) or other substance characteristics. The residual drug effect is generally accepted to be 5 times the terminal half-life. The terminal half-life of FE 204205 is anticipated to be within the range of 3 hours, i.e. in this study the residual drug effect is likely to be well within the time to the last assessment in both Part 1 and Part 2. Since this is the first time FE 204205 is administered to patients with cirrhotic portal hypertension, all AEs occurring from start of infusion on Day 1 up to the last assessment on Day 4 in Part 1 and Day 2 in Part 2 are regarded as treatment emergent.

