### Post-treatment Emergent Adverse Events

A post-treatment emergent adverse event is any AE occurring after the time of residual drug effect of the IMP, i.e. after the last assessment on Day 4 in Part1, and after Day 2 in Part 2.

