#### **Overview of treatment emergent adverse events**

A treatment emergent AEs (TEAE) overview summary table will be presented including for each treatment; the number of subjects reporting an AE, the percentage of subjects with an AE, and the number of events reported, for the following categories:

- All AEs
- Severe AEs
- SAEs
- Adverse drug reactions
- AEs leading to withdrawal
- Deaths

Adverse drug reactions (ADRs) are defined as events considered being reasonably possibly related to the IMP as judged by the Investigator.

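### AE summary tables stop the morning after the last dose, so SAEs and drug reactions that begin later, but before the follow-up visit, are listed but not counted by treatment

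*Combined protocol and SAP*

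**What the plan says.** Section 7.1.1 has AEs recorded from informed consent to the follow-up visit. Section 8.1 (Treatment Emergent Adverse Event) divides that period: AEs from the start of the Day 1 infusion "up to the last assessment on Day 4 in Part 1 and Day 2 in Part 2 are regarded as treatment emergent". Later events are post-treatment emergent, "i.e. after the last assessment on Day 4 in Part1, and after Day 2 in Part 2".

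Section 7.1.2 shows when those last assessments occur. In Part 1 vital signs are taken on the dosing days, "and in the morning of Day 4 as well as at the follow-up visit in Part 1"; in Part 2 they are taken on Day 1, "in the morning of Day 2, and at the follow-up visit". Tables 6-1 and 6-2 agree. The cut-off is thus the morning after the last dose. For Part 2, section 6.2 (Visit 3) says "A follow-up visit will be performed 4-11 days after the administration". Section 6.1 (Visit 3) gives Part 1 the same interval, counted from the last administration.

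On reporting, section 9.6.2.4 says "Only treatment emergent AEs will be presented in summary tables" and sends pre-treatment and post-treatment events to a separate listing. Under its overview subheading, "A treatment emergent AEs (TEAE) overview summary table will be presented including for each treatment"; the rows include SAEs, adverse drug reactions and deaths. The same section adds separate listings of SAEs, deaths and other significant AEs. It describes no table that counts events up to the follow-up visit.

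**The concern.** Safety and tolerability is the first objective listed in section 2.1. The overview is where a reader will look for the number of SAEs, drug reactions and deaths by treatment. As specified, those rows describe the infusion days plus the following morning, although patients remain under AE observation for several more days.

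The restriction reaches the drug-reaction row as well. Suppose the investigator judges an event that begins on Day 3 of Part 2 to be reasonably possibly caused by the IMP. It is still post-treatment by date, so it adds nothing to that row.

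The plan elsewhere treats late events as important. Section 8.5.1 wants deaths up to four weeks past treatment documented whatever their cause, and section 8.6.2 keeps related SAEs reportable however late they occur. A zero in the overview could be quoted as a finding for the whole trial when it covers only part of the observed period.

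**Working it through.** **Inputs.** Last dose: Day 3 in Part 1, Day 1 in Part 2 (section 5.1.1). Cut-off: morning of Day 4 and of Day 2 (sections 8.1 and 7.1.2). Follow-up: Days 7-14 and Days 5-12 (sections 6.1 and 6.2). Patients: 6 in Part 1; 16 active and 4 placebo in Part 2 (section 3.1.2).

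**1. The plan's own figure.** Follow-up day minus last-dose day: Part 1, 7 - 3 = 4 and 14 - 3 = 11; Part 2, 5 - 1 = 4 and 12 - 1 = 11. The stated 4-11 days is reproduced in both parts.

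**2. Uncounted interval.** Follow-up day minus cut-off day: Part 1, 7 - 4 = 3 and 14 - 4 = 10; Part 2, 5 - 2 = 3 and 12 - 2 = 10. So 3-10 days in both parts.

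**3. Share of post-dose time outside the tables.**

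| Counted from | Part 1 | Part 2 |
|---|---|---|
| Last dose | 3/4 = 75% to 10/11 = 91% | 3/4 = 75% to 10/11 = 91% |
| First dose | 3/6 = 50% to 10/13 = 77% | 3/4 = 75% to 10/11 = 91% |

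Section 8.1 leaves a small ambiguity for Part 2. One definition ends at the Day 2 assessment; the other starts the next category after Day 2. If the window ran to the end of Day 2, it would be shorter than 2 days after a morning dose, and the share outside would still exceed 2/4 = 50% to 9/11 = 82%.

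**4. Which events fall in the interval.** The rule works on onset. For an abnormal laboratory test or examination, section 8.2.2 (Date and Time of Onset) dates onset to the sample or examination. Follow-up includes a physical examination, vital signs, ECG and laboratory samples, and Table 7-1 includes creatinine and troponin I. A clinically significant abnormality first seen at follow-up is therefore post-treatment by rule, whenever the change began.

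**5. Effect on the overview.** Illustration, assuming one patient has an SAE that begins after the cut-off and before follow-up:

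| Group | Overview as planned | Counted to follow-up |
|---|---|---|
| Part 2, active | 0/16 | 1/16 = 6.3% |
| Part 2, placebo | 0/4 | 1/4 = 25% |
| Part 1 | 0/6 | 1/6 = 16.7% |

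**6. How likely that is.** The documents give no rate. If each patient independently has probability p of such an event (an assumption), the chance of at least one among n patients is 1 - (1 - p)^n:

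| p | 16 active | All 26 |
|---|---|---|
| 0.01 | 0.149 | 0.230 |
| 0.02 | 0.276 | 0.409 |
| 0.05 | 0.560 | 0.736 |
| 0.10 | 0.815 | 0.935 |

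**The case against.** The case for leaving the plan alone has real substance.

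- **Nothing is hidden.** Late events appear in the by-subject, post-treatment, SAE and death listings. With 26 patients a reader can count them. This stands, and it limits the point to the summary counts.
- **Much delayed harm would still be tabulated.** Sections 9.6.2.1 to 9.6.2.3 summarise vital signs, ECG and laboratory variables by treatment, and follow-up is one of the scheduled times. A renal, cardiac or haemoglobin change still present then would be visible. A reader might infer that the safety tables would show nothing of late effects; the documents do not support that.
- **Onset decides, not discovery.** A reader might infer that any SAE or death discovered at follow-up counts as zero. That is too strong. A symptom that began inside the window is still a TEAE, and section 8.2.2 has it recorded at its highest intensity. Section 8.5.1 treats death as an outcome, so a late death from an event that began inside the window may well be counted; the plan does not say. Only test and examination findings are dated by when they were made.
- **The window is reasoned.** Section 8.1 takes five half-lives of about 3 h, 5 x 3 = 15 h, and cites first use in these patients as the reason to count everything up to the last residential assessment. A reader might infer that the window is pharmacologically too short; no half-life in the documents shows that.
- **Little comparison is possible.** With 16 against 4 patients, one late event says almost nothing about a difference between arms. This stands; the added table is for description.
- **A separate SAP is announced in section 9.** It might contain such a table. If it does, the point is met, but section 9.6.2.4 as written allows only treatment-emergent events in summary tables.

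**Conclusion.** The point holds as a gap in the AE counts by treatment. Every AE summary table, including the SAE, adverse drug reaction and Deaths rows of the overview, is limited to events that begin by the morning after the last dose. Under the day arithmetic above, 75-91% of the time from last dose to follow-up lies outside the counts. An overview of zero SAEs or drug reactions could therefore be correct by its definition while such events occurred under observation.

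The percentages rest on whole-day counting with the cut-off one day after the last dose. They describe observation time, not the expected share of events, and the documents give no basis for saying that late events will occur. The TEAE definition itself is not shown to be wrong, and no data are lost. This is a cheap improvement, not an error that invalidates the safety analysis.

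**What to change.** Keep the TEAE definition and all planned TEAE tables. In section 9.6.2.4, add one overview by treatment of all AEs, SAEs, adverse drug reactions and deaths with onset from first dose to the follow-up visit, and exempt it from the rule that restricts summary tables to treatment-emergent events. State whether deaths are counted by date of death or by onset of the causal event, and apply the same rule to the Deaths row of the TEAE overview. Because Part 1 patients receive several doses, also state how a late event there is assigned to a treatment column, for example by last dose received or by dose cohort.

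The cost is one extra table from data already collected, with no added visits or samples. The downside is that some events due to the underlying cirrhosis will enter the longer window; the unchanged TEAE tables beside it keep the two periods distinguishable.
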